**ABBREVIATIONS**

AE	Adverse Event
AKI	Acute Kidney Injury
ATC	Anatomical-Therapeutic-Chemical
ATSP	Acute Transfusion Support Period
CMH	Cochran-Mantel-Haenszel
CI	Confidence Interval
Control	Conventional RBCs
CRO	Contract Research Organization
CSR	Clinical Study Report
eCRF	Electronic Case Report Form
IPCW	Inverse Probability of Censoring Weighting
MAR	Missing at Random
MCMC	Markov Chain Monte Carlo
MedDRA	Medical Dictionary for Regulatory Activities
MI	Multiple Imputation
MITT	Modified Intention To Treat
MMRM	Mixed Models for Repeated Measures
M&N	Miettinen and Nurminen
MNAR	Missing Not At Random
PMM	Pattern Mixture Modeling
PPS	Per-Protocol Set
PT	Preferred Term
RBC	Red Blood Cell
SAE	Serious Adverse Event
SAP	Statistical Analysis Plan
SAS	Statistical Analysis System
sCr	Serum Creatinine
SOC	System Organ Class
SROS	Study RBC Only Set
TE	Treatment Emergent
TEAE	Treatment Emergent Adverse Event
Test	INTERCEPT RBCs
TR	Transfusion Reaction
TRUST	Transfusion Risk Understanding Scoring Tool
US	United States

## 1. INTRODUCTION

This statistical analysis plan (SAP) specifies the statistical methods to be implemented for the analysis of data collected from the ReCePI study within the scope of Cerus' Protocol CLI 00125, "A Randomized, Double-Blinded, Controlled, Parallel Group, Non-inferiority, Phase III Study to Evaluate the Efficacy and Safety of the INTERCEPT Blood System for Red Blood Cells in Patients undergoing Complex Cardiac Surgery Procedures (the ReCePI study)." It applies to the study protocol (version 7.0) dated 20 December 2021 and provides detailed instructions as to how each analysis will be performed.

Results obtained from the analyses specified in the final approved version of the SAP will become the basis of the clinical study report (CSR) for this study. Post-hoc exploratory analyses not necessarily identified in this SAP may be performed to further examine study data. Any post-hoc, or unplanned, exploratory analysis will be clearly identified as such in the final CSR.

## 2. CLINICAL BACKGROUND

The ReCePI study is based on the premise that renal impairment within 48 hours of complex cardiac surgery is an indicator of inadequate tissue oxygenation and is a prognostic indicator that correlates with day 30 post surgery mortality (Lassnigg 2004, Lassnigg 2008). Renal hypoxia is a major determinant of renal impairment, measured as a change in the subjects' serum creatinine (sCr). Renal hypoxia may be caused by impaired renal blood flow, anemia, or qualitative dysfunction of red blood cells resulting in inadequate renal oxygenation. RBCs transfused to correct anemia are hypothesized to prevent renal hypoxia and impairment both by augmenting blood volume and by providing increased oxygen carrying capacity resulting in improved tissue oxygenation. This study is designed to demonstrate non-inferiority of INTERCEPT RBCs (Test) compared with conventional RBCs (Control) in preventing renal tissue hypoxia, as measured by the change in sCr from baseline prior to surgery to sCr levels within the 48-hour period following the completion of surgery.

It is not possible to evaluate the efficacy of transfused Test and Control RBCs in isolation, as study RBCs are naturally diluted by the patients' own blood during transfusion, as well as by re-transfused cell saver blood (a mixture of autologous and transfused RBCs) collected and transfused during surgery. In addition, the study protocol recognizes that cardiac surgery patients may unpredictably require large numbers of RBC components that exceed the available supply of RBCs prepared in accordance with the study protocol, resulting in the transfusion of non-study conventional RBC components. RBC transfusion under these circumstances is "per protocol", however, every effort has been made to avoid non-study RBC transfusions. Prevention of non-study RBC transfusions has proven a challenge. We assume that the use of non-study RBC will be random with respect to treatment assignment into the Test and Control groups as the manufacture of Test and Control RBC inventories has been balanced.

The use of cell-saver and non-study RBC transfusions is potentially problematic, and both the classical mITT and PP analyses study are subject to potential biases, despite execution of the study in compliance with the protocol.

As expected from prior literature review and confirmed by examination of blinded study data, the risk of the primary endpoint (AKI) and increasing number of RBCs transfused during the acute study transfusion period are proportional to the complexity and duration of the cardiac surgery procedures performed and the patients underlying condition and disease prior to surgery. Patients who receive larger numbers of RBC transfusions are more likely to meet the primary efficacy endpoint and are also more likely to receive non-study RBC transfusions per protocol due to a requirement for large volume or massive transfusions. For these reasons, the mITT analysis set best represents an assessment of the efficacy of Test RBCs, despite the inclusions of subjects who receive non-study RBCs within the 48 hours post-surgery analysis period of the primary efficacy endpoint.

The SAP presents the primary non inferiority analysis as performed on the mITT analysis set that will include all randomized subjects transfused with any type of RBC component during or within 48 hours of surgery, including those who receive non-study RBCs and autologous cell-saver RBCs in addition to study RBC transfusion(s). Various sensitivity analyses using the mITT analysis set are proposed to assess the robustness of the primary analysis.

Additional exploratory analyses on two subpopulations are presented for comparison purposes: First, a Per Protocol Set (PPS) that excludes important protocol deviations but includes cell saver and non-study RBC transfusions given as described in the protocol. Second, a Study RBC Only Set (SROS) that includes subjects who received only study RBCs (and cell saver RBCs) according to the randomization assignment within the 48-hour post-surgery primary endpoint assessment period. Analyses will be performed to determine the effect of including incremental numbers of non-study RBC transfusions. For the purposes of the statistical analysis plan,  $\geq 4$  RBC units related to an 8-hour surgery and  $\geq 10$  units of RBCs within 24 hours represents larger volume or massive transfusion, respectively.

### **3. OBJECTIVE(S) AND ENDPOINTS**

#### **3.1 Objectives**

The objective of this study is to evaluate the efficacy and safety of red blood cell (RBC) transfusion for support of acute anemia in cardiovascular surgery patients based on the clinical outcome of renal impairment following transfusion of RBCs treated with the INTERCEPT Blood System for Red Blood Cells (INTERCEPT RBCs) compared to patients transfused with conventional RBCs.

### 3.2 Endpoints

#### 3.2.1 Primary Efficacy Endpoint

The primary efficacy endpoint is:

- Any raised sCr level, occurring after transfusion of a study RBC, of  $\geq 0.3$  mg/dL (or  $26.5$   $\mu$ mol/L) from the pre-surgery baseline within  $48\pm4$  hours of the end of surgery.

#### 3.2.2 Secondary Efficacy Endpoints:

- The incidence of Stage I, II or III Acute Kidney Injury (KDIGO 2012) based on changes in sCr levels from pre-surgery baseline and the need for renal replacement therapy (RRT) post-surgery.
- Mortality or the need for RRT by 30 days post-surgery.

#### 3.2.3 Safety Endpoints

The primary safety endpoints are:

- Proportion of patients with any treatment-emergent adverse events (TEAEs) possibly, probably, or definitely related to study RBC transfusion through 28 days after the last study transfusion.
- Proportion of patients with treatment emergent (TE) antibodies with confirmed specificity to INTERCEPT RBCs by end of study (i.e.,  $75\pm15$  days after the last study transfusion).

Additional safety assessments will include:

- Treatment-emergent AEs through 28 days after the last study transfusion.
- Treatment-emergent SAEs through 28 days after the last study transfusion.
- Transfusion reactions (as defined by the CDC National Healthcare Safety Network [NHSN] Hemovigilance Module protocol) through 28 days after last study transfusion.
- Treatment-emergent immunization to RBC alloantigens through  $28\pm3$  days after the last study transfusion.
- Treatment-emergent immunization to HLA alloantigens through  $28\pm3$  days after the last study transfusion.

Please note no formal hypotheses will be tested on the primary safety endpoints.

## 4. STUDY DESIGN

### 4.1 General Study Design

The study is a prospective, multicenter, randomized, double-blinded, active controlled, parallel-design, non-inferiority study.

[figure not shown]
Subjects with high likelihood to received a transfusion as determined by the investigator and who meet eligibility criteria at Screening can be randomized up to 7 days before or on the day of surgery, but prior to the start of surgery.

Randomized subjects will receive as clinically indicated and determined by the treating physician only study RBCs during the Acute Transfusion Support Period (ATSP), starting from surgery till post-operative Day 7, hospital discharge or death, whichever is first.

Following the ATSP, Subjects will return for Day 28 and Day 75 Visits after last study transfusion.

At least 292 eligible subjects will be randomized and transfused with study RBC(s) (Figure 1).

**Figure 1: Study Design Diagram**

#### 4.2 Randomization and Blinding

Subject will be randomized with a 1:1 ratio to receive either INTERCEPT RBCs (Test) or conventional RBCs (Control). Randomization will be stratified by site, pre-existing renal impairment ( $sCr \geq 1.2 \text{ mg/dL}$  vs.  $< 1.2 \text{ mg/dL}$ ), and surgery procedure based on less vs. more risk for renal complications due to surgical complexity. The randomization schedule is generated and implemented by an independent CRO.

Randomized subjects who do not receive any study RBC transfusions from randomization to within the first 48 hours after completion of surgery will be discontinued from study and replaced.

This is a double-blinded study. The subjects, operating room staff, surgical staff, ICU staff and others caring for participating patients, as well as the sponsor (and delegates) will be blinded to treatment assignment. Only appropriate blood bank staff and unblinded delegates who monitor the production of the RBC components will be able to access the treatment arm assignment. Selected Blood Center staff will not be blinded due to their role required for collection, preparation, and releasing of Test and Control RBC components for transfusion to study subjects.

#### 4.3 Sample Size Estimation

By assuming the proportion of patients with  $\Delta sCr \geq 0.3 \text{ mg/dL}$  to be 30% in the Control arm and no more than a 50% increase from the Control rate (15%) as the non-inferiority margin, a sample size of  $\geq 292$  patients (146 per arm) will provide approximately  $\geq 80\%$  power to declare non-inferiority at the two-sided 0.05 alpha level, assuming the true treatment difference is zero.

Under the same assumptions, sample sizes of 334 patients (167 per arm) and 392 patients (196 per arm) will provide 85% and 90% power, respectively.

In order to maintain sufficient study power to establish non-inferiority for the primary efficacy endpoint, Cerus plans to transfuse a minimum of 320 subjects and may go up to 400.

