### 10.1 Analyses of Primary Endpoint

#### 10.1.1 Primary Analyses

The primary efficacy endpoint is the proportion of patients with a diagnosis of renal impairment defined as any raised sCr level, occurring after transfusion of a study RBC, of  $\geq 0.3$  mg/dL (or 26.5  $\mu$ mol/L) from the pre-surgery baseline within  $48 \pm 4$  hours of the end of surgery.

The corresponding hypothesis is:

$$H_0: P_{Test} - P_{Control} \geq 50\% \times \hat{P}_{Control}$$

*versus*

$$H_A: P_{Test} - P_{Control} < 50\% \times \hat{P}_{Control},$$

where  $P_{Test}$  and  $P_{Control}$  are the event rates for Test (INTERCEPT) and Control groups, respectively, and  $\hat{P}_{Control}$  is the observed Control rate.

The primary analysis of the primary efficacy endpoint will be based on Miettinen and Nurminen (M&N) method stratified by baseline sCr ( $sCr \geq 1.2 \text{ mg/dL}$  vs.  $< 1.2 \text{ mg/dL}$ ) and cardiac surgery group performed (more at risk for renal complications vs. less at risk) based on the observed cases.

The maximum observed post-baseline sCr value will be used to calculate the increase from baseline. If subjects have no post-baseline sCr within 48 hours post-surgery at all, this subject will be treated as missing the primary endpoint.

The common risk difference in proportions and the Mantel-Haenszel score 95% CI for the treatment difference (Test – Control) will be calculated using the stratified M&N method adjusting for baseline sCr and cardiac surgery group type. The estimate of the common risk difference will be calculated based on the stratum risk differences across all strata (Agresti, 2002; p. 231). Non-inferiority will be claimed if the upper bound of the 2-sided M&N Score 95% CI for the treatment difference (Test – Control) is less than 50% of the observed Control rate. Further, if the upper bound is less than 0, then superiority is achieved.

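### The stated 80%, 85% and 90% power hold for a fixed 15-point margin; the planned test, with a margin of half the observed Control rate, gives about 75%, 79% and 85%

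*SAP*

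**What the plan says.** SAP section 4.3 takes the event proportion "to be 30% in the Control arm" and sets "no more than a 50% increase from the Control rate (15%) as the non-inferiority margin". Testing is "at the two-sided 0.05 alpha level" with a true difference of zero. On that basis 292 subjects (146 per arm) give approximately 80% power or more, and 334 (167 per arm) and 392 (196 per arm) "will provide 85% and 90% power, respectively". To protect power, "Cerus plans to transfuse a minimum of 320 subjects and may go up to 400".

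SAP section 10.1.1 fixes the test. "Non-inferiority will be claimed if the upper bound of the 2-sided M&N Score 95% CI for the treatment difference" (Test minus Control) "is less than 50% of the observed Control rate". The hypotheses are written with the same quantity: the Control rate that defines the margin "is the observed Control rate".

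Section 7.4 records that a blinded re-estimation reduced the sample size from 600 to at least 292, and section 4.1 repeats 292 as the minimum.

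**The concern.** The two sections describe different tests. In 4.3 the margin is the number 0.15. In 10.1.1 it is half of a proportion estimated from the trial's own Control arm, so it varies from sample to sample. The two sources of error also compound: when the observed Control rate happens to be low, the margin shrinks and the observed Test-minus-Control difference rises at the same time. Section 4.3 makes no allowance for this, so its powers cannot be those of the planned analysis.

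At stake is the justification for the enrolment range. The minimum of 320 is presented as a size that keeps power sufficient, and readers will take 80% as secured from 292 upwards. If it is not, the chance that a truly equivalent product fails to show non-inferiority is larger than the plan states.

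**Working it through.** **Inputs.** All are from SAP sections 4.2, 4.3 and 10.1.1: Control rate 0.30; Test rate 0.30 (true difference zero); 1:1 allocation; upper bound of a two-sided 95% interval, so z = 1.96; margin 0.15 in 4.3 and 0.5 × observed Control rate in 10.1.1. Write n for subjects per arm and pq = 0.30 × 0.70 = 0.21.

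**Step 1: reproduce the plan's figures with a fixed margin.** Power = Φ(0.15/√(2 × 0.21/n) − 1.96).

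- n = 146: 0.15/0.05364 − 1.96 = 0.837, so 79.9%
- n = 167: 0.15/0.05015 − 1.96 = 1.031, so 84.9%
- n = 196: 0.15/0.04629 − 1.96 = 1.280, so 90.0%

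Exact enumeration of all binomial outcome pairs with the unstratified Miettinen-Nurminen bound gives 80.2%, 85.1% and 90.2%. The stated powers are therefore those of a fixed 15-point margin.

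**Step 2: apply the rule in 10.1.1.** Non-inferiority is claimed when p̂T − p̂C + 1.96·SE < 0.5·p̂C, that is, when p̂T − 1.5·p̂C + 1.96·SE < 0. The statistic p̂T − 1.5·p̂C has mean −0.15 and variance (1 + 2.25)pq/n = 3.25 × 0.21/n. The SE in the bound still reflects only 2 × 0.21/n. Hence

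Power ≈ Φ((0.15 − 1.96·√(2 × 0.21/n)) / √(3.25 × 0.21/n)).

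For n = 146: (0.15 − 1.96 × 0.05364)/0.06837 = 0.656, so 74.4%. The other sizes follow in the same way.

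| Total | Stated | Fixed 15 points, exact M&N | Rule in 10.1.1, formula | Rule in 10.1.1, exact M&N |
|---|---|---|---|---|
| 292 | about 80% | 80.2% | 74.4% | 74.9% |
| 320 | – | 83.7% | 77.6% | 78.0% |
| 334 | 85% | 85.1% | 79.1% | 79.4% |
| 392 | 90% | 90.2% | 84.2% | 84.5% |
| 400 | – | 90.7% | 84.9% | 85.3% |

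**Step 3: sizes that the written rule needs.** Setting the formula equal to the target gives √n = (1.96·√0.42 + z·√0.6825)/0.15.

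- 80% (z = 0.842): n = 172, total 344
- 85% (z = 1.036): n = 201, total 402
- 90% (z = 1.282): n = 242, total 484

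Exact enumeration is slightly more favourable: about 340 (80.1%), 398 (85.1%) and 480 (90.2%).

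**Step 4: effect of stratification.** The planned interval is stratified, but the SAP gives no stratum sizes or rates. Two assumed sets were simulated with a stratified Mantel-Haenszel Wald bound. Both used four strata with shares 30/25/25/20%. Stratum rates were 20/28/34/42% (overall 29.9%) in one set and 15/25/35/50% (overall 29.5%) in the other.

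| Total | Fixed 15 points | Rule in 10.1.1 |
|---|---|---|
| 292 | 81.8% to 83.8% | 76.2% to 77.1% |
| 334 | 86.4% to 88.4% | 80.5% to 81.5% |
| 392 | 91.2% to 92.7% | 85.5% to 86.4% |

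Like for like, the gap remains about 5 to 7 points. Linear interpolation at 320 gives 76.2 + (14/21) × 4.3 = 79.1% and 77.1 + (14/21) × 4.4 = 80.0%.

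**Step 5: the error rate at which this power is bought.** With true rates of 45% and 30%, the edge of the null hypothesis, the rule in 10.1.1 claims non-inferiority in 5.9% to 6.0% of trials (exact M&N), against a nominal one-sided 2.5%. The cause is the same: the interval ignores the margin's variance. A test of pT − 1.5·pC that carries the full variance has lower power. By the Wald formula Φ(0.15/√(0.6825/n) − 1.96), it is 59.2% at 292, 63.2% at 320 and 72.8% at 400. A score test with restricted estimates gives 61.9%, 65.5% and 75.3%.

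**The case against.** Five points can be made for the plan.

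- **The arithmetic is right for 15 points, and 4.3 says only approximately.** True, but 10.1.1 does not test 15 points. The word approximately attaches to the 80% figure alone and cannot cover a gap of 5 to 6 points.
- **292 is a floor, and the trial plans 320 to 400.** This stands in part. Over that range the written rule gives 78.0% to 85.3%, so the minimum misses 80% by two points in the unstratified calculation and by a point or less under the assumed strata. The upper end clears 80% but not 90%.
- **The exact figures are unstratified.** Correct, and the SAP gives nothing from which to do better. The assumed strata raise both sets of powers by a few points and leave the gap.
- **The link to the cut from 600 is not documented.** Section 7.4 attributes the cut to a blinded re-estimation without showing the calculation. That the powers in 4.3 underlie it is a reasonable inference, no more.
- **Planning power does not enter the estimate, the interval or the claim.** Also correct. Low power makes a false failure more likely and does not weaken a positive result. The inflated error in Step 5 is the more serious consequence of the same margin definition, and if that is cured by fixing the margin at 15 points, this point disappears too. Until one section is changed, 4.3 states powers that the specified test does not have.

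**Conclusion.** The concern holds, and section 4.3 must be corrected or 10.1.1 aligned with it. The shortfall against the stated powers is about 5 to 6 points at each of the three sizes. The 320 minimum is at or just below 80%, and 90% lies outside the planned range because it needs about 480 subjects.

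The figures rest on a true event rate of 30% in both arms, equal arms, every transfused subject evaluable for the endpoint, and an unstratified Miettinen-Nurminen bound. Stratification shifts the levels by one to two points under the written rule for the strata assumed, without closing the gap.

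**What to change.** Choose the test first, then make 4.3 and 10.1.1 agree before unblinding. There are three consistent options.

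1. **Fixed margin.** State in 10.1.1, in both the hypotheses and the decision rule, that the margin is 15 percentage points. The powers in 4.3 then stand. This also returns the one-sided error at 45% against 30% to about 2.5%.
2. **Keep the observed-rate rule.** Restate 4.3 as about 75%, 79% and 85% at 292, 334 and 392, and about 78% to 85% over 320 to 400. Say that these are unstratified, or name the stratum assumptions used. The excess type I error remains and would need its own remedy.
3. **Test the relative margin with its full variance.** Name the method in 10.1.1 and give its power in 4.3. For a restricted-estimate score test of pT − 1.5·pC this is about 62%, 66% and 75% at 292, 320 and 400; a Wald version is about two to three points lower.

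Each option is a change of SAP wording. None by itself requires more subjects. Under options 2 and 3 the stated power becomes less favourable, and the sponsor would then have to decide whether 320 remains an adequate minimum.

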#### 4.4 Visits and Assessments

Assessments at each visit and the time/visit window for each post-baseline assessment are specified in the Assessment Schedule ([Table 1](#)). For subjects whose study participation is terminated prior to Day 75 Visit, to the extent possible, physical exam, including general neurological examination, should be performed, concomitant medications and adverse events should be recorded. Standard laboratory tests should be collected, and other blood samples should be performed at the Exit Visit.

**Table 1: Assessment Schedule**

Study Period	Screening / Randomization		Acute Transfusion Support Period (Surgery to Post-operative Day 7, hospital discharge or death, whichever is first)		Follow-up Visits		
	Screening visit	Baseline (Pre-surgery)	Day 0 Surgery	Days 1 – 7, hospital discharge or death			
Assessment	Window	Day -30 to Day 0	pre-surgery	Day 0 Surgery	Days 1 – 7, hospital discharge or death	28±3 days After last study transfusion or Early Termination	30 days After Surgery
Informed Consent /Assent	X						
Demographics	X						
Indication / Type of scheduled surgery	X						
Medical, surgical, transfusion and medication history including radiographic contrast media within 7 days of surgery / the need for irradiated RBC products	X						
Number of prior pregnancies (females)	X						
Physical examination including height and weight	X						
TRUST score components	X						
Randomization	X #						
Vital signs (HR, BP, RR)	X 	X 	X	X 	X		
Concomitant medications	X	X 	X 	X 	X		
Weekly telephone calls							
EKG	X 	X 	X 	X 			
Pregnancy test (if applicable)	X 	X 					
Hematology panel	X 	X 	X 	X 	X 		
Blood chemistry	X 	X 	X 	X 	X 		
Blood type	X 						
Serum Creatinine at 48±4 hours after end of surgery				X			
Hemodynamic Parameters		X 	X 	X 			
Fibrinogen, Troponin		X 	X 	X 			
Urine output			X 	X 			
Procedure details			X				
Study RBC crossmatch and Study RBC transfusion(s)/data			X	X			

Study Period	Screening / Randomization		Acute Transfusion Support Period (Surgery to Post-operative Day 7, hospital discharge or death, whichever is first)		Follow-up Visits			
	Screening visit	Baseline (Pre-surgery)	Day 0 Surgery	Days 1 – 7, hospital discharge or death				
Assessment	Window	Day -30 to Day 0	pre-surgery	Day 0 Surgery	Days 1 – 7, hospital discharge or death	28±3 days After last study transfusion or Early Termination	30 days After Surgery	End of Study (75±15 days After Last Study Transfusion)
DAT, IAT	X 			X 	X 	X		
INTERCEPT RBC antibody screen (S-303-specific antibody screen)	X			X 	X 	X		X
Sample for HLA antibodies	X					X		
All other blood components (including non- study RBCs) transfused, if any				X	X	X		
Estimated blood loss from surgery				X				
Estimated blood loss from other source including chest tube(s)					X 			
AEs/SAEs/TRs	X*	X*	X*	X*, 		X ^		
Documentation of vital status and need for RRT						X	X 	X

1. For Screening/Randomization purposes, data from medical records within 30 days prior to their surgical procedure may be used.
2. See protocol Table 7.2: Hematology and Chemistry Testing for details on required labs.
3. These assessments can be combined with screening assessments if screening visit is also on Day -1 or Day 0 Pre-Surgery.
4. Data collected on eCRFs only as available from medical records if performed as Standard of Care.
5. Hemodynamic Parameters: Peripheral O2 Saturation, Mean Arterial Pressure, Central Venous Pressure.
6. These assessments are required to be collected daily on Day 1 through Day 7 post surgery or until discharge. If subject returns after discharge for a postoperative standard of care visit, assessments will be collected in eCRFs on the appropriate study day.
7. Any drugs given to induce anesthesia or drugs given as a prophylactic in combination with anesthesia prior to surgery do not need to be recorded. Medications given during anesthesia to treat an AE/SAE need to be recorded.
8. Urine output data collected daily while a urinary catheter is in place. The date entered should reflect the start of the collection and match the visit date.
9. S-303 screen must be performed whenever a routine RBC alloantibody screen (IAT) is performed during the transfusion period.
10. Laboratory results recorded in the eCRFs during this period will only be those assessed as clinically significant by the Investigator.
11. Assess at Day 30 post surgery via clinic visit, medical record, or phone call. Any RRT that is provided prophylactically during surgery while the subject is on a bypass machine does not meet this endpoint.
12. # Eligible patients will be randomized up to 7 days before or on the day of surgery, but prior to the start of surgery (i.e., induction of anesthesia).
13. \* The adverse event, serious adverse event and transfusion reaction collection period will begin at the start of surgery or the first study RBC transfusion, whichever is first.
14. ^ The adverse event, serious adverse event and transfusion reaction collection period will begin at the start of surgery or the first study RBC transfusion, whichever is first. AEs including protocol specified AEs, TRs and SAEs (see protocol Section 7.3) are collected through 28 days after the last study transfusion; also collected daily during acute transfusion support period.

